9.1.2. Unsolicited Adverse Events

An unsolicited AE is an AE that was either not included in the list of solicited events using a Participant Diary or could be included in the list of solicited events but with an onset more than 7 days following administration of a study intervention.

The number and percentage of participants reporting unsolicited AEs classified by MedDRA primary SOC and PT will be summarized along with exact 95% CIs during:

- The 14-day post-vaccination period after each and any vaccination visit for all study groups and
- The 30-day post-vaccination period after each and any vaccination visit. It should be noted that participants in the HZ/suSeq and FluD-QIVSeq groups will receive their HZ/su or Flu D-QIV, respectively, at Day 14 post mRNA booster vaccine dose at Day 1.

Summaries of unsolicited AEs within the 14-day window following Dose 1 and 30-day window following each dose and overall will also be presented for all subgroups defined in Section 4.4.

Unsolicited AEs will also be summarized by intensity (any grade and Grade 3), any related to study vaccine, Grade 3 related, Grade 3 non-serious, Grade 3 non-serious related, AEs resulting in a medically-attended visit, and related AEs resulting in a medically-attended visit.

Summaries of medically-attended unsolicited AEs and related medically-attended unsolicited AEs within the 14-day and 30-day windows following Dose 1 of HZ/su and mRNA-1273 vaccination and following Flu D-QIV and mRNA-1273 vaccination will be presented for all subgroups defined in Section 4.4. The other AE summaries will be presented for age strata subgroups defined in Section 4.4.

9.1.3. Serious Adverse Events

The number and percentage of participants reporting SAEs and fatal SAEs from first vaccination up to 30 days post-last vaccination and from first vaccination up to study end will be summarized for all study groups (HZ/suSeq, HZ/suCoAd, FluD-QIVSeq, FluD-QIVCoAd and overall). Any related SAEs will also be summarized for all study groups (HZ/suSeq, HZ/suCoAd, FluD-QIVSeq, FluD-QIVCoAd and overall). All SAEs will be summarized by MedDRA SOC and PT. Fatal SAEs will be presented by onset day and day of death, for both any fatal SAEs and any related fatal SAEs in the data listing. SAEs, fatal SAEs and withdrawals due to SAEs will also be listed.

Summaries of SAEs up to 30 days post-last vaccination and from first vaccination up to study end will also be presented for all subgroups defined in Section 4.4. The other SAE summaries will also be presented for age strata subgroups defined in Section 4.4.

9.1.4. Potential Immune-mediated Diseases (for HZ/su and mRNA-1273 booster cohort only)

pIMDs include autoimmune diseases and other inflammatory and/or neurologic disorders of interest which may or may not have an autoimmune etiology. See Table 23 of study protocol dated 21September 2021, for a list of potential pIMDs.

The number and percentage of participants reporting pIMDs on the CRF from first vaccination up to 30 days post-last vaccination and from first vaccination up to study end will be summarized for both study groups in the HZ/su and mRNA-1273 booster cohort (HZ/suSeq, HZ/suCoAd, overall). All pIMDs will be summarized by MedDRA SOC and PT. Any related pIMDs will also be summarized for study groups (HZ/suSeq, HZ/suCoAd and overall).

Summaries of pIMDs from first vaccination up to study end will also be presented for all subgroups defined in Section 4.4. Summaries of pIMDs and related pIMDs up to 30 days post-last vaccination and related pIMDs from first vaccination up to study end will also be presented for age strata subgroups defined in Section 4.4.

All pIMDs will be listed.

9.1.5. Adverse events of special interest (AESI)

The number and percentage of participants reporting AESIs on the CRF from first vaccination up to 30 days post-last vaccination and from first vaccination up to study end will be summarized for all study groups. All AESIs will be summarized by MedDRA SOC and PT.

Summaries of AESIs from first vaccination up to study end will also be presented for all subgroups defined in Section 4.4. Summaries of AESIs and related AESIs up to 30 days post-last vaccination and related AESIs from first vaccination up to study end will also be presented for age strata subgroups defined in Section 4.4.

A listing of AESIs will also be presented.

9.1.6. Suspected HZ episodes (for HZ/su and mRNA-1273 booster cohort only)

The number and percentage of participants reporting the following:

- Suspected HZ episodes,
- With at least one lesion sample collected for suspected HZ episode, and
- Confirmed HZ episode

from first dose to study end will be summarized for the HZ/suSeq and HZ/suCoAd study groups. All potential HZ episodes and lesion sampling throughout the entire study period will be listed.

9.1.7. Confirmed HZ episodes (for HZ/su and mRNA-1273 booster cohort only)

Number and percentage of participants reporting clinically confirmed HZ cases by PCR from first vaccination up to study end will be summarized for all study groups (HZ/suSeq, HZ/suCoAd, and overall). The analysis of this data will be restricted to the cases where lesion sample is taken and will follow the suspected HZ episodes discussed in Section 9.1.6.

9.1.8. COVID-19 cases

COVID-19 cases identified during the study (as per standard of care) will be captured and reported using standard AE, medically-attended AE or SAE criteria, and routine procedures.

Diagnosis and categorization of COVID-19 cases for reporting purposes would be made in accordance with the following primary and secondary [Baden, 2021], and tertiary case definitions:

Primary Case Definition:

- The participant must have experienced at least TWO of the following systemic symptoms: fever (temperature $\geq 38^{\circ}\text{C}$), chills, myalgia, headache, sore throat, new olfactory and taste disorder(s), OR
- The participant must have experienced at least ONE of the following respiratory signs/symptoms: cough, shortness of breath or difficulty breathing, OR clinical or radiographical evidence of pneumonia; AND
- The participant must have at least one nasopharyngeal (NP) swab, nasal swab, or saliva sample (or respiratory sample, if hospitalized) positive for SARS-CoV-2 by PCR

Secondary Case Definition:

Defined as the following systemic symptoms: fever (temperature $\geq 38^{\circ}\text{C}$), or chills, cough, shortness of breath or difficulty breathing, fatigue, muscle aches or body aches, headache, new loss of taste or smell, sore throat, nasal congestion or rhinorrhea, nausea or vomiting, or diarrhea AND a positive NP swab, nasal swab, or saliva sample (or respiratory sample, if hospitalized) for SARS-CoV-2 by PCR

Tertiary Case Definition:

Documented diagnosis of COVID-19 made by a health care provider and not meeting the primary or secondary case definitions.

COVID-19 cases by primary case definition, secondary case definition, and tertiary case definition identified on the CRF AE pages will be summarized by number and percentage of participants from first dose to study end for all study groups (HZ/suSeq, HZ/suCoAd, FluD-QIVSeq, FluD-QIVCoAd and overall) and COVID-19 cases will also be listed.

9.1.9. Pregnancies

A listing of participants with confirmed pregnancies from first dose to study end will be provided for all study groups along with pregnancy details from the notification eCRFs.

9.1.10. Medical Device Deficiencies

One of the study interventions, the seasonal influenza vaccine, Flu D-QIV, is presented as a pre-filled syringe and according to the FDA regulations [FDA, 2018] is within scope of device reporting in clinical trials as a combination product constituted of a device and biologic product (e.g., pre-filled syringes).

Medical device AE will be recorded on the AE forms as adverse device effect (ADE), serious adverse device effect (SADE) and unanticipated SADE (USADE) and summarized by the number and percent of participants that experience a given event.

10. Safety analysis for Safety Review Team review

The safety review team (SRT) will first review safety and reactogenicity data reported up to 7 days post-dose 1 of HZ/su when 10% of participants in the HZ/suCoAd group and 7 days post Flu D-QIV when 5% of participants in the FluD-QIVCoAd group have been vaccinated. PPD preclarus dashboard will also be used to generate the required outputs for SRT review to help decide on continuation of enrollment in the co-administration groups. Periodic analyses will be done for regular SRT review. All SRT analyses will be descriptive.

Limited safety analyses will be performed after all participants in the HZ/su and mRNA-1273 booster cohort sequential group have completed 14 days of follow-up after their HZ/su dose 1, and when all participants in the Flu D-QIV and mRNA-1273 cohort sequential group have completed 14 days of follow-up after their Flu D-QIV dose. The outputs selected for limited safety analyses will be programmed as TFL outputs using SAS® software version 9.4 or later.

11. Interim Analysis

One formal interim analysis (IA) of safety and reactogenicity data was conducted. The safety objectives were assessed independently for the two cohorts (HZ/su and mRNA-1273 booster, Flu D-QIV and mRNA-1273 booster) at the IA when the last active participant enrolled in both cohorts complete their 6 weeks post-last dose of study vaccine Phone Contact 1.

Analyses were performed on data as clean as possible and an interim report was provided. The IA included:

- Solicited AE data after each administered vaccine dose (All groups: All doses of Flu D-QIV and mRNA-1273 booster dose; and all doses of HZ/su).

- Unsolicited AEs (serious and non-serious) safety data up to 30 days follow-up post each dose (All groups; including post all doses of Flu D-QIV and mRNA-1273 booster dose; and post all doses of HZ/su).
- SAEs, pIMDs, AESIs, suspected HZ episodes, IMCs, COVID-19 cases and pregnancies until the Data Lock Point (DLP) for all groups.

No hypothesis testing was conducted as part of the safety IA.

The final analysis will include safety follow-up up to 6 months post the last vaccine dose.

No IA was conducted for the immunogenicity data for either cohort as this data was not available at the timepoints set for the safety and reactogenicity data IA.

12. Changes in the Planned Analysis

Since the immunogenicity results were not available in time, the interim analysis was restricted to safety and reactogenicity data and did not include immunogenicity data as was originally planned per protocol.

The solicited systemic eDiary was unable to be programmed to shut off post-day 7 following vaccination assuming there were no ongoing events reported, which meant that these events were solicited daily for 30 days post-vaccination, even if they were not ongoing after 7 days post-vaccination. Since, as per protocol, any adverse event with an onset more than 7 days and up to 30 days post-vaccination was to be reported as an ‘unsolicited AE’, the AEs meeting this definition entered in the eDiaries were transcribed by the site staff to the unsolicited AE eCRF page and will be subsequently analyzed as such and not counted as solicited AEs in the safety analyses.

In Table 4 of the protocol, interval ranges between certain visits were provided whereby if the visits were to happen beyond these specified intervals, participants may not have been eligible for inclusion in the applicable Per Protocol Set (PPS). The out of window intervals in Table 8 and Table 9 below represent the actual limits that will be used in the final analyses.

Table 8 Intervals between study visits for HZ/su and mRNA-1273 booster cohort

Interval	Planned Visit Interval	Allowed Interval Range to Remain in PPS
		HZ/suSeq group
Pre-vaccination → Visit 1	-7 days	No impact on PPS
Visit 1→Visit 2	14 days	13-49
Visit 1→Visit 3	28 days	25-49
Visit 2→Visit 4	28 days	No impact on PPS
Visit 2→Visit 5	56 days	48-83
Visit 5→Visit 6	28 days	25-49
Visit 5→Phone contact 1	42 days	No impact on PPS

Interval	Planned Visit Interval	Allowed Interval Range to Remain in PPS
Visit 5→Phone contact 2	168 days	No impact on PPS
HZ/suCoAd group		
Pre-vaccination → Visit 1	-7 days	No impact on PPS
Visit 1→Visit 2	28 days	25-49
Visit 1→Visit 3	56 days	48-83
Visit 3→Visit 4	28 days	25-49
Visit 3→Phone contact 1	42 days	No impact on PPS

Table 9 Intervals between study visits for Flu D-QIV and mRNA-1273 booster cohort

Interval	Planned Visit Interval	Allowed Interval Range to Remain in PPS
FluD-QIVSeq group		
Pre-vaccination → Visit 1	-7 days	No impact on PPS
Visit 1→Visit 2	14 days	13-42 days
Visit 1→Visit 3	28 days	21-42 days
Visit 2→Visit 4	28 days	21-42 days
Visit 2→Phone contact 1	42 days	No impact on PPS
Visit 2→Phone contact 2	168 days	No impact on PPS
FluD-QIVCoAd group		
Pre-vaccination → Visit 1	-7 days	No impact on PPS
Visit 1→Visit 2	28 days	21-42 days
Visit 1→Phone contact 1	42 days	No impact on PPS
Visit 1→Phone contact 2	168 days	No impact on PPS

13. References

U.S. Food and Drug Administration (FDA). Combination Product Definition Combination Product Types. Content current as of 15 February 2018. <https://www.fda.gov/combination-products>

products/about-combination-products/combination-product-definition-combination-product-types. Accessed on 16 June 2021

14. Appendices

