Blood sampling for antibody determination		Refer to Table 2 for blood sampling schedule for each group (●)									
HZ lesion sample (HZ/su and mRNA-1273 booster cohort only)	Unscheduled visits (●)									Refer to Table 3 for procedures to be followed	
Record any concomitant medications/vaccinations		●	●	●	●	●	●	●	●		
Record any intercurrent medical conditions (IMC)		●	●	●	●	●	●	●	●		
Phone contact for safety follow-up								●	●		

CONFIDENTIAL

217670 (ZOSTER-091)
Protocol Amendment 1 Final

Type of contact	Pre-Vacc	Visit 1	Visit 2	Visit 3	Visit 4	Visit 5	Visit 6	Phone Contact 1	Phone Contact 2	Notes	
Timepoint	-7 days	Day 1	Week 2	Week 4	Week 6	Week 10	Week 14	6 weeks post last dose	24 weeks post last dose		
			Week 4	Week 8	Week 12						
			Week 2	Week 4	Week 6						
			Week 4								
Training participants to recognize signs and symptoms of HZ (HZ/su and mRNA-1273 booster cohort only)		○	○	○	○	○	○				
Recording of solicited AEs: onset post-study intervention administration (day of and following 6 days)		Refer to Table 2 for the schedule for each group (●)									
Review/Return of eDiary		○	○	○	○	○	○				
Recording of non-serious AEs within 30 days post-dosing		●	●	●	●	●	●				
Recording of SAEs, AESIs, COVID-19 cases, and pregnancies. In addition, pIMDs and suspected HZ episodes in the HZ/su and mRNA-1273 booster cohort		●	●	●	●	●	●	●	●		
Recording of AEs/SAEs related to study participation, or SAEs related to concurrent GlaxoSmithKline medication/vaccine	●	●	●	●	●	●	●	●	●	To be recorded if the event onset occurs any time after signing the ICF	
Recording of withdrawals		●	●	●	●	●	●	●	●		
Study Conclusion								●			

AE = adverse event; AESI = adverse event of special interest eDiary = electronic diary; HZ= Herpes Zoster; IMC = intercurrent medical condition; PCR = polymerase chain reaction; pIMD = potential immune mediated disease; SAE = serious adverse event

Grey cells indicate the given activity is not planned for the corresponding timepoint(s)

The double-line border following Phone contact 1 indicates an interim analysis

● is used to indicate a study procedure that requires documentation in the individual electronic case report form

○ is used to indicate a study procedure that does not require documentation in the individual electronic case report form

CONFIDENTIAL

217670 (ZOSTER-091)
Protocol Amendment 1 Final

Table 2 Schedule of study intervention administration and blood sampling for the study groups

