8.3. Adverse events (AEs), serious adverse events (SAEs) and other safety reporting

8.3.1. Time period and frequency for collecting AE, SAE and other safety information

The timeframes for collecting and reporting the safety information are provided in [Table 14](#).

Table 14 Timeframes for collecting and reporting of safety information

EVENT	TIMING OF REPORTING
Local and systemic solicited events	Day 1 through Day 7 following each study intervention administration (see Figure 1)
Unsolicited AEs	Day 1 through Day 30 following each study intervention administration (see Figure 1)
AEs/SAEs leading to withdrawal from the study	Day 1 following study intervention administration through Phone Contact 2 study conclusion
All SAEs including SAEs related to the study intervention	Day 1 following study intervention administration through Phone Contact 2 study conclusion
AEs/SAEs related to study participation or SAEs related to concurrent GlaxoSmithKline medication/vaccine	Enrollment (i.e., signing ICF) through Phone Contact 2 study conclusion
IMCs, AESIs, COVID-19 cases, and in HZ/su and mRNA-1273 booster cohort only, also pIMDs and suspected HZ episodes	Day 1 following study intervention administration through Phone Contact 2 study conclusion
Pregnancy	Day 1 through Phone Contact 2 study conclusion

The investigator or designee will record and immediately report all SAEs/AESIs/pIMDs/pregnancies in study participants to PPD via the Expedited AE Reporting Form or pregnancy form (as applicable). Reporting should, under no circumstances, occur later than 24 hours after the investigator becomes aware of an SAE/AESI/pIMD/pregnancy, as indicated in Section [10.2.12](#). The investigator will submit any updated SAE/AESI/pIMD/pregnancy data to PPD within 24 hours of it being available.

A post-study AE/SAE is defined as any event that occurs outside of the AE/SAE reporting periods defined in [Table 14](#). Investigators are not obligated to actively seek AEs or SAEs from former study participants. However, if the investigator learns of any SAE, including a death, at any time after a participant has been discharged from the study, and he/she considers the event to be reasonably related to a study intervention, the investigator will promptly notify the study contact for reporting SAEs mentioned in [Table 16](#).

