Shivering/chills
Fever
Gastrointestinal symptoms (nausea, vomiting, diarrhea and/or abdominal pain)
Arthralgia

Note: Participants will be instructed to measure and record the body temperature, preferably in the evening, using the temperature measuring device provided by GSK/PPD. The recommended route of temperature measurement will be the oral route. If additional temperature measurements are taken at other times of the day, participants will be instructed to record the highest temperature in the eDiary.

10.2.4. **Unsolicited AEs**

An unsolicited AE is an AE that was either not included in the list of solicited events using a Participant Diary or could be included in the list of solicited events but with an onset more than 7 days following administration of a study intervention. Unsolicited events must have been communicated by a participant who has signed the informed consent. Unsolicited AEs include both serious and non-serious AEs.

Potential unsolicited AEs may be medically attended (i.e., symptoms or illnesses requiring a hospitalization, or an emergency room visit, or visit to/by a health care provider). The participants will be instructed to notify the site as soon as possible to report medically attended events, as well as any events which, though not medically attended, are of participant's concern or which prevent the participant from normal daily activities. Detailed information about reported unsolicited AEs will be collected by qualified site personnel and documented in the participant's records.

Unsolicited AEs that are not medically attended, perceived as a concern by the participant, nor prevented normal daily activities, will still be collected during an interview with the participants and by review of available medical records at the next visit.

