9.1.1. Solicited Adverse Events

Solicited AEs are pre-specified local and systemic adverse events. Solicited AEs will be collected through 7 days following each vaccination. Solicited AEs with onset during the 7-day solicitation period that continue beyond the 7-day period will be reported as solicited AEs. The solicited AEs will be collected using the diary eCRFs.

Participant's compliance with respect to the diary card based on the Exposed Set will be determined separately for local and systemic events for the following:

- Number of participants who did not present diary data at all
- Number of participants who completed diary card, regardless of visit
- Number of participants who completed diary card for each day of the first 7 days post any vaccination (i.e., Day 1, Day 2, Day 3, Day 4, Day 5, Day 6 and Day 7)

A sensitivity analysis to exclude participants who may not have acceptable diary data or certain missing diary records may be performed.

Per the study design and diary forms, participants who receive the administration of the mRNA-1273 booster vaccine on Day 1, have until Day 14 (Week 2) to receive the next vaccine administration. As such, all solicited systemic AEs that occurred on or after mRNA-1273 booster vaccine but prior to HZ/su or Flu D-QIV vaccine administration on Day 14 (Week 2) are deemed to be attributable to the mRNA-1273 booster vaccine. For participants in the sequential groups (HZ/suSeq, FluD-QIVSeq), the diary forms are re-set at the time of first HZ/su or Flu D-QIV vaccination on Day 14 (Week 2) to collect solicited systemic AEs that are either ongoing from mRNA-1273 booster vaccine from Day 1 or occurred on or after the first HZ/su or Flu D-QIV vaccination on Day 14 (Week 2). The diary data is therefore setup to ensure that any solicited systemic AE attributable to each of the following vaccines only: mRNA-1273 booster, first HZ/su, second HZ/su or Flu D-QIV, can be determined depending on the time of the AE relative to the time of each vaccine administration, and prior to the date of any subsequent vaccination. Solicited local AEs are collected in separate diaries per vaccine received and will be attributed to the appropriate based on the diary used.

For data analysis purposes, the CoAd groups (HZ/suCoAd, FluD-QIVCoAd) will be presented as a single column, with the exception of the HZ/suCoAd group that certain selected outputs will be displayed by the first and second HZ/su vaccine doses respectively.

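### Systemic symptoms prompted daily to Day 30 enter the unsolicited AE tables unflagged, with about 7 more prompted days in the sequential arms at the planned schedule

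*SAP*

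**What the plan says.** The protocol solicits systemic symptoms on the day of each vaccination and the following 6 days (Section 1.3, Table 1). It collects unsolicited AEs from "Day 1 through Day 30 following each study intervention administration" (Section 8.3.1, Table 14). Its definition of an unsolicited AE (Section 10.2.4) includes a symptom that "could be included in the list of solicited events but with an onset more than 7 days following administration of a study intervention". The same section describes how unsolicited AEs are found. Participants report medically attended, worrying or activity-limiting events to the site, and the rest "will still be collected during an interview with the participants and by review of available medical records at the next visit".

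SAP Section 12 (amended SAP) discloses that the systemic eDiary could not be programmed to stop after Day 7, so "these events were solicited daily for 30 days post-vaccination, even if they were not ongoing after 7 days post-vaccination". Entries with onset after Day 7 were "transcribed by the site staff to the unsolicited AE eCRF page and will be subsequently analyzed as such".

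SAP Section 9.1.2 tabulates unsolicited AEs over 14 and 30 days, after each vaccination visit and after any visit, with splits by intensity, relatedness and medical attendance. It has no source flag and no version without the transcribed events. The only diary-related sensitivity analysis (SAP Section 9.1.1) is optional and concerns unacceptable or missing diary data. SAP Section 9.1.1 also says that in the sequential groups the diary is re-set when HZ/su or Flu D-QIV is given at Week 2.

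**The concern.** A daily prompt naming fatigue, headache, myalgia and similar symptoms finds more of them than an interview at the next visit does. The unsolicited tables will therefore mix two ascertainment methods, one for the prompted systemic terms and another for everything else, and a reader cannot tell which events came from which.

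The prompted time also differs between the arms being compared. The sequential arms have one more vaccination visit, so the diary runs longer in them. With equal underlying rates, the any-visit rows would show more prompted events in the sequential arms, which are the comparator. Protocol Section 4.2 says the safety data are meant to help authorities give guidance on co-administration, so a tilt in that direction is worth removing.

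**Working it through.** The plan gives no figure for prompted days by arm or for symptom rates, so there is none to reproduce. The check counts calendar days.

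**Inputs**
- Prompting: Days 1-30 after each vaccination (SAP Section 12).
- Solicited window: Days 1-7 after each vaccination (Protocol Section 1.3).
- Planned gap from booster to second visit in the sequential arms: 14 days (Protocol Tables 4 and 5). With the booster on Day 1, the next vaccine falls on Day 15.
- HZ/su dose 2: 56 days after HZ/su dose 1 in both HZ arms (Protocol Table 4).
- Diary re-set at the second visit (SAP Section 9.1.1), so the 7 days from that visit are treated as a new solicited week.

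**Schedule check.** Last-dose week plus 24 weeks gives 10 + 24 = 34 (HZ/suSeq) and 2 + 24 = 26 (FluD-QIVSeq). These match the approximate durations in Protocol Section 4.1.

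**Rule.** A day feeds the unsolicited tables if it lies on Days 8-30 after some dose and not on Days 1-7 after another.

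**30-day any-visit tables, planned gap**
- FluD-QIVCoAd: Days 8-30 = 23.
- FluD-QIVSeq: Days 8-14 (7) + Days 22-44 (23) = 30. Ratio 30/23 = 1.30.
- HZ/suCoAd (doses on Days 1 and 57): Days 8-30 (23) + Days 64-86 (23) = 46.
- HZ/suSeq (doses on Days 1, 15 and 71): 7 + Days 22-44 (23) + Days 78-100 (23) = 53. Ratio 53/46 = 1.15.

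The excess is 7 days in both cohorts.

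**14-day any-visit tables.** Only Days 8-14 after each dose count, 7 days per visit. Flu: 2 × 7 = 14 against 7. HZ: 3 × 7 = 21 against 2 × 7 = 14.

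**Sensitivity to the gap (30-day tables)**

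| Gap, Visit 1 to Visit 2 | Flu Seq vs CoAd | HZ Seq vs CoAd | Excess |
|---|---|---|---|
| 13 days | 29 vs 23 | 52 vs 46 | +6 |
| 14 days | 30 vs 23 | 53 vs 46 | +7 |
| 21 days | 37 vs 23 | 60 vs 46 | +14 |
| 30 days or more | 46 vs 23 | 69 vs 46 | +23 |

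The protocol window is 14-21 days. The SAP's per-protocol limits are wider: 13-42 days (Flu) and 13-49 days (HZ). The safety tables use the Exposed Sets, so those limits do not bound the gap there.

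**Sensitivity to the re-set rule.** If the new solicited week also counted as unsolicited time after the booster, the planned-gap figures would be 37 vs 23 and 60 vs 46.

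**Illustration with assumed rates.** Suppose a proportion p of FluD-QIVCoAd has at least one prompted event over 23 days, and the daily rate is constant and equal in both arms. Then FluD-QIVSeq shows 1 − (1 − p)^(30/23):
- p = 10%: 1 − 0.90^1.304 = 12.8%.
- p = 25%: 1 − 0.75^1.304 = 31.3%.

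**The case against.** Four points on the other side carry weight.

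- **The classification is the protocol's own.** A listed symptom with onset after Day 7 is unsolicited by definition, and the SAP discloses the eDiary departure. This stands. A reader might infer that the events are misclassified, or that the unsolicited tables were meant for spontaneous reports only. The documents support neither, since interview and record review were always part of collection. What changed is the intensity of ascertainment.
- **The sequential arms have an extra visit by design.** Their any-visit window would be longer with a working eDiary too. This also stands: the fault adds daily prompting to an existing imbalance.
- **Other planned outputs limit the damage.** In the 14-day per-visit tables both arms have the same Days 8-14 at the planned gap. Tables by preferred term leave fatigue, headache and myalgia visible, and Grade 3, related and medically attended splits are planned. This confines the between-arm problem mainly to the any-visit rows, but no output separates prompted from unprompted reports of the same term.
- **The safety analyses are descriptive.** No hypothesis test is affected, which limits the importance of the point.

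A reader might also count total prompting, 44 against 30 days (Flu) and 74 against 60 (HZ), and conclude that the sequential arms have 14 extra days. Those totals include the solicited Days 1-7 after each dose, which do not feed the unsolicited tables. At the planned gap the relevant excess is 7 days.

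**Conclusion.** The point holds as a low-cost improvement. Prompted late-onset systemic symptoms go into the unsolicited tables unflagged, so rates for those symptoms may be inflated relative to unprompted collection. Only the systemic eDiary is named, so local symptoms are outside the point.

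At the planned schedule the sequential arms have about 7 more prompted days feeding the any-visit tables. The relative imbalance is largest in the 14-day Flu table, at twice the days. Longer gaps between visits widen the 30-day excess. The direction would tend to favour co-administration in those rows.

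The day counts rest on the planned schedule, full 30-day prompting after every dose, and the re-set week being treated as solicited. The 10-25% rates are assumed; the documents give none. A reader might therefore go further and conclude that prompted symptoms will dominate the unsolicited tables, or that comparison with other data on these products is lost. The documents contain nothing that would support either.

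**What to change.** In SAP Sections 9.1.2 and 12:

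1. Flag every systemic event with onset after Day 7 that was transcribed from the eDiary.
2. Keep the unsolicited AE tables as the protocol defines them, so that no event is hidden.
3. Add a version of those tables that excludes the flagged events.
4. Tabulate the flagged events separately by group, over matched post-dose windows or per prompted person-day.

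The cost is a source flag and a second version of the unsolicited AE tables. SAP Section 9.1.1 says the diary data already hold events within 7 days and events beyond 7 days separately, which should help in identifying the transcribed ones. SAP Section 1 places finalisation of the amendment before final database lock, which is the natural point to specify the flag.
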